3.3 Planned Analyses

The statistical analysis plan includes the methods and types of the analysis, the variables the data sets and the timeframe when the (interim) analysis is planned. Recall that participants will be completing three repetitions of each stimulus. Repetitions will be averaged within each participant prior to analysis. Reliability within each participant will also be assessed to determine if that participant's data should be included the analysis.

- Repeated-measures analysis of variance (RM-ANOVA) to detect significant effects
- Post-hoc pairwise comparisons to locate the source of significant effects

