Study Protocol and Statistical Analysis Plan

Speech Locator In-car Performance Evaluation— ID# SRF-459

Jan 27, 2022

NCT05054816

Speech Locator In-car Performance Evaluation—ID# SRF-459

1 Objectives and hypotheses of the clinical investigation

1.1 Purpose of the clinical investigation claims for clinical performance, effectiveness or safety of the investigational device that are to be verified

The insight on general and individual preferences between the investigational feature and comparator features will be used to determine if and when the investigational feature should be included in an upcoming platform release. The initial clinical evaluation of the development of this feature has been requested by Research & Development.

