Overall impression ratings: Participants will be instructed to "All things considered, please rate overall preferences". Overall preferences ratings will be measured on a 100-point continuous slider from worst to best (0-Bad, 25-Poor, 50-Fair, 75-Good, 100-Excellent). Overall impression ratings are expected to be impacted by participants' overall preferences for the different stimuli. Participants will rate and compare overall impression between the investigational and comparator features.

Transition annoyance ratings: Participants will be instructed to "Please rate how annoying the transitions are". Transitions annoyance ratings will be measured on a 100-point continuous slider from worst to best (0-Extremely annoying, 25-Very annoying, 50-Moderately annoying, 75-Slightly annoying, 100-Not at all annoying). Transition annoyance ratings are expected to be influenced by presence of unexpected sounds or transitions that occur in different microphone modes and different listening situations. Participants will rate and compare transition annoyance between the investigational and comparator features.

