3.3.1 Datasets to be analyzed, analysis population

Analysis population: 15-25 participants

Evaluation group: rating per setting

Data sets: subjective ratings

- Additional analyses:
 - Individual preferences and their potential dependences, such as hearing loss,

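### Averaging the three repetitions before analysis, with no exemption for the individual-preference analysis, leaves no way to separate a listener's preference from rating noise

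*Combined protocol and SAP*

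**What the plan says.** Section 1.1 gives the purpose: "The insight on general and individual preferences between the investigational feature and comparator features" will inform whether and when the feature goes into a release. Section 3.3.1 then lists, among additional analyses, "Individual preferences and their potential dependences, such as hearing loss". It names no method, and the item ends on a comma, so it may be incomplete.

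Section 3.3 describes the data and their handling: "Recall that participants will be completing three repetitions of each stimulus", and "Repetitions will be averaged within each participant prior to analysis". The next sentence adds: "Reliability within each participant will also be assessed to determine if that participant's data should be included the analysis". No reliability metric or cut-off is given. The methods listed are "Repeated-measures analysis of variance (RM-ANOVA) to detect significant effects" and post-hoc pairwise comparisons, both at group level. Sections 3.3.2 and 3.3.3 add only who analyses the data, when, and in which software.

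**The concern.** Once the repetitions are averaged, each listener has one number per condition. A listener may score the investigational feature higher because of a real preference or because three slider ratings happened to fall that way. The averaged data cannot tell these apart. The three repetitions can, but the averaging rule, followed as written, keeps them out of the individual-preference analysis.

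At stake is how individual results are read. Apparent groups of listeners who like or dislike the feature could be largely noise, and preferences would look more varied than they are. Section 1.1 says individual preferences feed the release decision.

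**Working it through.** **Inputs from the plan.** Three repetitions per stimulus, averaged within participant, then RM-ANOVA (Section 3.3). "Analysis population: 15-25 participants" (Section 3.3.1), with 20 listeners named in Section 1.2. For overall impression, "Overall preferences ratings will be measured on a 100-point continuous slider from worst to best" (Section 2.1.3). The plan states no SD, effect size, significance level or number of conditions, so there is no figure to reproduce.

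**Assumptions.** σw is the SD of a listener's repeated ratings of the same condition, taken as 5, 10, 15 or 20 points. σLC is the SD of the true listener-by-condition effect. k is the number of conditions. Each condition mean rests on exactly three ratings, and data are complete and balanced.

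**1. Group comparison.** With all ratings kept and listener-by-condition as the error term, the condition and error mean squares are each three times their values from the averages, so F is the same. A simulated data set with 20 listeners, k = 3 and three repetitions gave F = 7.93 both ways. Averaging costs nothing here.

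**2. Dependence on hearing loss.** With two conditions, this is a regression of each listener's mean difference on hearing loss. Rating noise sits in the outcome and is carried by the residual. In balanced data the slope and its test are the same from averaged or unaveraged ratings.

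**3. Individual preferences.** From averages alone, the residual variance is

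σLC² + σw²/3.

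Only the sum can be estimated. Three very different situations give the same value:

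| σLC | σw | σLC² + σw²/3 |
|---|---|---|
| 0 | 15 | 0 + 225/3 = 75 |
| 5 | 12.25 | 25 + 150/3 = 75 |
| 8.66 | 0 | 75 + 0 = 75 |

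In each, a listener's two-condition difference varies around the group mean with SD √(2 × 75) = 12.2 points. In the first row all of that is noise; in the last, all of it is preference.

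**4. Size of the noise.** With no true individual preference and no mean difference, a listener's difference D between two three-rating means has SD σw × √(2/3), and P(|D| > 10) = 2 × [1 − Φ(10/SD)].

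| Assumed σw | SD of D | P(\|D\| > 10) | Expected of 20 listeners |
|---|---|---|---|
| 5 | 4.1 | 1% | 0.3 |
| 10 | 8.2 | 22% | 4.4 |
| 15 | 12.2 | 41% | 8.3 |
| 20 | 16.3 | 54% | 10.8 |

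The 10-point mark is a yardstick for this illustration, not a rule in the plan.

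**5. What keeping the repetitions buys.** The within-listener error then has n × k × (3 − 1) degrees of freedom: 20 × 3 × 2 = 120, or 15 × 2 × 2 = 60. The listener-by-condition mean square has expectation σw² + 3σLC² and can be tested against σw². At an assumed level of 0.05 and σLC²/σw² = 0.25, power is 0.70 for n = 20, k = 3 and 0.41 for n = 15, k = 2. At a ratio of 0.5 it is 0.96 and 0.72. With pooled error (n = 20, k = 2 or 3), one listener's difference must exceed about 1.62 × σw to differ from zero at the 95% level. For σw = 10 that is 1.62 × 10, about 16 points.

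**The case against.** The strongest reply is that the averaging sentence stands directly above the RM-ANOVA and post-hoc items and may be meant only for them. On that reading the plan has merely left the individual method unspecified. This is possible, but the sentence carries no such limit, and nothing elsewhere gives an error term for an individual listener. The gap remains on either reading.

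A reader might infer that within-listener information is thrown away before any analysis. The documents do not support that: the reliability assessment in Section 3.3 needs the unaveraged repetitions. It does not close the gap, though, because it decides inclusion and gives no uncertainty for the listeners who are kept.

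A reader might also infer that the hearing-loss analysis is compromised. It is not, as step 2 shows.

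The illustration can fairly be called severe. The plan sets no 10-point cut-off and no rule for classing listeners. A reliability screen would tend to remove the noisiest raters, which makes the SD of 20 the least likely case to remain. If a preference pooled two stimuli per condition, which the plan does not say, the noise SD would be divided by √2. For σw = 10, 15 and 20 it becomes 5.8, 8.7 and 11.5 points, and the shares above 10 points fall to 8%, 25% and 39%. These points make the size uncertain; they do not supply the missing error term.

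Finally, individual preference is in neither objective of Section 1.2. That limits the reach of the point, but Section 1.1 still ties it to the release decision.

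**Conclusion.** The point holds for individual preferences only. Followed as written, the plan overstates the spread of individual preferences whenever there is rating noise, and gives no uncertainty for any single listener's difference. This part is algebra and needs no assumed SD.

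The size does depend on assumptions. The share of listeners with an apparent difference above 10 points from noise alone runs from 1% at a repetition SD of 5 to 54% at 20, with three ratings per condition and no true preference. These figures are illustrative and do not forecast a misclassification rate.

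It would be too strong to conclude that the study cannot learn about individual preferences. The limit lies in the analysis as written, not in the design: three repetitions are enough to estimate within-listener error. The group RM-ANOVA and the test of dependence on hearing loss are unaffected.

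**What to change.** Limit the averaging sentence in Section 3.3 to the group RM-ANOVA. Under the additional analyses in Section 3.3.1, state that individual preferences are analysed from the unaveraged ratings. One suitable choice is a linear mixed model with condition fixed, participant and participant-by-condition random, and repetition as residual. Report the participant-by-condition variance and each listener's difference with an interval. Simple per-listener intervals based on pooled within-listener error would also supply the missing uncertainty. The hearing-loss analysis can stay on averaged differences.

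The cost is a sentence or two in the plan and a little extra work in R, which the plan already uses. No new data are needed, and the balanced group results do not change.

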1.2 Primary and Secondary Objectives

The primary objective of this study is to measure the subjective impression of the investigational feature (using overall impression and listening effort ratings) in 20 experienced hearing aid users with mild to severe hearing loss.

The second objective is to determine if there are any audible artifacts while implementing the feature, and if there are, measure how bothersome they are to the listener.

2 Design of the clinical investigation

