2.1.3 Endpoints with rationale for their selection and measurement

Ratings are expected to be different among different test conditions. An internal evaluation has been completed with normal hearing employees, who reported audible differences for all selected sound dimensions. Rationales for the specific rating dimensions are as the following:

Speech clarity ratings: Participants will be instructed to "Please rate the clarity of speech". Speech clarity ratings will be measured on a 100-point continuous slider from worst to best (0-Very unclear, 25-Unclear, 50-Slightly clear, 75-Clear, 100-Very clear). Speech clarity ratings are expected to be impacted by how intelligible the speech is. Participants will rate and compare speech clarity between the investigational and comparator features.

Noise annoyance ratings: Participants will be instructed to "Please rate how annoying the noise is". Noise annoyance ratings will be measured on a 100-point continuous slider from worst to best (0-Extremely annoying, 25-Very annoying, 50-Moderately annoying, 75-Slightly annoying, 100-Not at all annoying). Noise annoyance ratings are expected to be impacted by how bothersome the background

noise in the recordings is. Participants will rate and compare noise annoyance between the investigational and comparator features.

Spatialization ratings: Participants will be instructed to "Please rate your confidence that the talker is in [a location]", with the local being either passenger of rear left. Spatialization ratings will be measured on a 100-point continuous slider from worst to best (0-I don't know where the talker is, 25-The talker might be to my [location], 50-The talker is probably to my [location], 75-The talker is to my [location], 100-The talker is definitely to my [location]). Spatialization ratings are expected to be impacted by how well the recordings preserve spatial perception. Participants will rate and compare spatialization between the investigational and comparator features.

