3.2 Statistical criteria of termination of trial

If the results are significant after 15 participants have completing the protocol, we will consider terminating the data collection.

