3.3.2 Primary Analysis

The study manager will analyze the collected data set in R Statistics after the data collection is completed. Microsoft Excel and MATLAB may be used for arranging data and plotting data sets.

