3.3.3 Secondary Analysis

The study manager will analyze the collected data set in R Statistics after the data collection completed.

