3.3.4 Interim Analysis

The study manager will analyze the collected data set in R Statistics in real time as the data collection is completed. Microsoft Excel and MATLAB may be used for arranging data and plotting data sets.

4 Informed consent process

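### One of the two primary ratings has no scale, and the significant result that may stop the study at 15 participants is never defined

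*Combined protocol and SAP*

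**What the plan says.** **Objective.** Section 1.2 defines the primary objective as the subjective impression of the feature, measured "using overall impression and listening effort ratings". The second objective concerns audible artifacts and how much they bother the listener.

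**Endpoints.** Section 2.1.3 opens its list with "Rationales for the specific rating dimensions are as the following" and gives a prompt and a 0-100 slider for five ratings: speech clarity, noise annoyance, spatialization, overall impression and transition annoyance. For overall impression it states the comparison: "Participants will rate and compare overall impression between the investigational and comparator features". The other four have parallel sentences.

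**Analysis.** Section 3.3 lists "Repeated-measures analysis of variance (RM-ANOVA) to detect significant effects" and post-hoc pairwise comparisons. Section 3.3.2 (primary) says "The study manager will analyze the collected data set in R Statistics after the data collection is completed" and adds that other software may be used to arrange and plot data. Section 3.3.3 (secondary) says "The study manager will analyze the collected data set in R Statistics after the data collection completed". Neither names a rating, model factor, contrast or threshold. Section 3.3.1 gives an analysis population of 15-25 and refers to ratings by setting.

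**Stopping.** Section 3.2 says termination will be considered under this condition: "If the results are significant after 15 participants have completing the protocol". Section 3.3.4 has the data analysed "in real time as the data collection is completed".

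**The concern.** There are two linked gaps. First, listening effort is half of the primary objective but has no prompt, scale or planned collection, so the objective cannot be met as written. Second, the analysis sections do not carry a primary rating forward from 1.2 and give no significance level or adjustment, yet the stopping rule depends on significance. With five ratings, an unstated number of comparators and settings, and no fixed number of looks, two analysts could reach opposite stopping decisions from the same data and both claim to have followed the plan.

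This matters because section 1.1 uses the results to decide whether and when the feature goes into a product release. An unadjusted optional stop raises the chance that a feature with no real advantage appears to have one. Choosing which result counts after seeing the data raises it further.

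**Working it through.** **Step 1. Objective against endpoints.**

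| Rating | Named in 1.2 | Prompt and scale in 2.1.3 |
|---|---|---|
| Overall impression | yes | yes |
| Listening effort | yes | no |
| Speech clarity, noise annoyance, spatialization, transition annoyance | no | yes |

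The term listening effort occurs once in the document, in 1.2, and no redaction mark appears at these points.

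**Step 2. The plan's own figure.** Section 3.1 allows up to 25 participants including up to 5 pilots; 25 - 5 = 20, which agrees with the 20 in 1.2. Nothing more can be reproduced, because no significance level, power, effect size or SD is given. The final n is open between 15 and 25 (3.3.1).

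**Step 3. One contrast on one rating.** Assumptions not in the plan: two-sided 0.05, no true difference, normally distributed paired differences. At each look, t = mean difference / (SD/√n), rejecting if |t| exceeds the 97.5% point of t with n - 1 degrees of freedom. A false positive is a rejection at any look. From 400,000 simulated null trials:

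| Looks | 0.05 at every look | p<0.001 before the final analysis, 0.05 at the end |
|---|---|---|
| 20 only | 5.0% | - |
| 15 and 20 | 7.5% | 5.0% |
| 15 and 25 | 8.1% | 5.1% |
| every participant, 15 to 20 | 9.4% | 5.0% |
| every participant, 15 to 25 | 11.9% | 5.0% |

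As a check, the normal approximation for two looks has correlation √(15/20) = 0.87 or √(15/25) = 0.77 between looks and gives 7.3% and 8.0%. A repeat simulation agreed within 0.1 percentage point.

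**Step 4. Five ratings.** One RM-ANOVA per rating, 2 to 4 conditions, equal correlation between ratings, 20,000 null trials per cell, 0.05 per test:

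| Correlation | Any rating, one analysis (20 or 25) | Any rating, 15 and 20 | Any rating, 15 and 25 | All five at 15 |
|---|---|---|---|---|
| 0 | 22.2-23.5% | 32.0-33.2% | 34.4-35.3% | 0.00% |
| 0.5 | 18.3-19.1% | 26.5-27.4% | 28.5-29.2% | 0.02-0.06% |
| 0.8 | 13.0-13.7% | 19.0-19.6% | 20.4-20.9% | 0.60-0.74% |

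Check at correlation 0 with one analysis: 1 - 0.95^5 = 22.6%.

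**Step 5. What control would cost in power.** These figures use the noncentral t distribution with noncentrality d√n, where d is the true difference in SDs of the paired difference. The smallest d detectable with 80% power at n = 20, at the first Holm step 0.05/k:

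| Tests in family, k | Level | d |
|---|---|---|
| 1 | 0.05 | 0.66 |
| 2 | 0.025 | 0.74 |
| 4 | 0.0125 | 0.81 |
| 8 | 0.00625 | 0.89 |

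For d = 0.66, the chance of crossing at n = 15 is 66% at p<0.05 and 12% at p<0.001.

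**The case against.** The plan is not without an order. Section 1.2 ties the primary objective to overall impression, which is fully defined, and transition annoyance plausibly serves the second objective. On that reading the any-rating figures describe something the plan does not intend, and the relevant inflation is modest: 5% to about 7.5-8.1%. The stop is discretionary, 3.2 names a single milestone, and the real-time phrase in 3.3.4 may only mean analysis on completion. Section 1.1 describes an initial evaluation requested by Research & Development, for which strict error control may be more than is needed. Section 3.3 also recalls three repetitions per stimulus that are not mentioned before, so a fuller internal protocol may exist, and listening effort may be a leftover label.

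Much of this is fair. The single-rating figure is the one closest to the documents, the five-rating figures are only bounds, and the look-after-every-participant figures hold only under one reading of 3.3.4. The missing listening-effort scale is also a separate gap from the undefined stop.

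The core remains. Section 3 never carries the order of 1.2 forward. An optional unadjusted stop still inflates error when it is used. The plan nowhere calls itself descriptive or exploratory; it ties a stop to significance and a release decision to the results. The published document must also be usable without an internal one.

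**Conclusion.** The concern holds. As written, half of the primary objective has no measure, and the result that may end data collection at 15 is undefined in rating, contrast, level and number of looks. On the narrowest reading (one contrast on overall impression, one look at 15) the false-positive rate is about one and a half times nominal. Repeated looks bring it to roughly twice nominal. Reading the stop as any one of five ratings gives the worst case in the working. Requiring all five at 15 makes a false stop very unlikely (at most 0.7%). That spread, from under 1% to about 35%, shows how much depends on choices the plan leaves open.

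All rates rest on an assumed two-sided 0.05 per test and no true differences; the five-rating figures also assume 2 to 4 conditions and correlations of 0 to 0.8. The single-contrast rates leave out any further inflation from several post-hoc pairs. The inconsistency between 1.2 and 2.1.3 needs no assumption. This should be corrected before data are seen.

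**What to change.** 1. **Sections 1.2 and 2.1.3.** Remove listening effort from the primary objective, or define its prompt and scale, collect it and add it to the primary family.
2. **Section 3.3.2.** Make the within-participant investigational-versus-comparator contrast on overall impression primary, at a stated two-sided 0.05, with 95% confidence intervals. Use Holm adjustment if there is more than one comparator. Say whether the contrast is pooled over settings or made per setting; if per setting, those contrasts join the Holm family. The RM-ANOVA can stay as the model from which the contrast is taken.
3. **Section 3.3.3.** Label the other ratings secondary or exploratory, and say whether transition annoyance is the measure for the second objective.
4. **Sections 3.2 and 3.3.4.** Allow at most one look, at 15, on the primary contrast at a strict threshold (for example p<0.001, with 0.05 at a stated final n), or drop significance-based stopping. If the family has several contrasts, say which must cross. An equal level at both looks, about 0.033 (final n of 20) or 0.031 (final n of 25), would also hold 0.05 for one contrast.
5. **Alternative.** If the study is meant to be purely descriptive, say so, label all p-values exploratory and remove the significance-based stop.

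**Cost.** Dropping listening effort needs wording changes in 1.2, 3.2 and 3.3 only, though it does narrow the stated objective. Keeping it adds a rating task for each participant and raises the detectable difference at n = 20 from 0.66 to 0.74 SD; further comparators or settings raise it more, and pooling settings avoids part of that. With p<0.001 at 15, early stopping becomes uncommon even for a real difference of 0.66 SD. Ratings outside the primary family face stricter thresholds or are exploratory.

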3.1 Determination of Sample Size

We will recruit up to 25 participants, including up to 5 pilot participants. Previous research with subjective ratings has repeatedly shown that data collected with 15-25 participants can yield significant results.

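### Section 3.3 names no investigational-versus-comparator contrasts: after the omnibus test, unrestricted post-hoc pairs lose power if adjusted over all pairs, or lose error control with four or more conditions if unadjusted

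*Combined protocol and SAP*

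**What the plan says.** Section 3.3 of the combined protocol and SAP lists two inferential steps. The first is "Repeated-measures analysis of variance (RM-ANOVA) to detect significant effects". The second is "Post-hoc pairwise comparisons to locate the source of significant effects". As worded, the second step follows from a significant first step. It is not limited to particular pairs, and no adjustment is named. Sections 3.3.2 to 3.3.4 add only the analyst, the software and the timing.

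The question to be answered is in section 1.1, where "The insight on general and individual preferences between the investigational feature and comparator features will be used to determine" whether and when the feature goes into a platform release. Section 2.1.3 describes the comparison in the same way for each of the five ratings, for example "Participants will rate and compare overall impression between the investigational and comparator features". Comparators are plural throughout.

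Section 3.2 lets significant results after 15 completed participants prompt consideration of ending data collection. It does not say which test has to be significant.

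**The concern.** An omnibus test asks whether any conditions differ. The release decision asks whether the investigational feature differs from each comparator. With two or more comparators these are different questions, and the follow-up step does not bring the analysis back to the second one.

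There are two possible costs. If the pairs are adjusted as one family, part of the error rate goes on comparator-versus-comparator pairs that the release decision does not use. If they are not adjusted, a significant omnibus result caused by one poor comparator permits a set of unprotected feature tests. In addition, a significant omnibus result on its own says little about the feature, yet section 3.2 as written could accept it as grounds for stopping at the smallest planned sample.

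**Working it through.** **The plan's own figure.** Section 3.1 supports 15-25 participants by appeal to earlier research. It gives no alpha, power, effect size or SD, so there is nothing to reproduce.

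**Inputs from the documents.** Comparators are plural, so on a plain reading there are at least k = 3 conditions. The analysis population is 15-25. Repetitions are averaged, giving one value per listener and condition.

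**Inputs assumed.** Two-sided alpha 0.05; k = 3 to 6; compound-symmetric errors; SD of paired differences 15; feature 12 points better than every comparator (standardised difference 12/15 = 0.80); Holm wherever an adjustment is applied. Results are simulated with at least 20,000 runs per case, so a power near 50% carries a 95% simulation error of about 1.96 × √(0.5 × 0.5/20,000) = 0.7 points.

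**Size of the two families.** All pairs number k(k−1)/2 and feature contrasts number k−1. For k = 3/4/5 that is 3/6/10 against 2/3/4, so 1/3/6 pairs do not involve the feature. The first Holm threshold is 0.05/3, 0.05/6, 0.05/10 = 0.0167, 0.0083, 0.0050 over all pairs, against 0.05/2, 0.05/3, 0.05/4 = 0.0250, 0.0167, 0.0125 over feature contrasts.

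**Power for one given feature contrast, n = 15.**

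| Procedure | k=3 | k=4 | k=5 |
|---|---|---|---|
| Omnibus, then Holm over all pairs | 68% | 56% | 47% |
| Holm over all pairs, no omnibus condition | 69% | 57% | 47% |
| Omnibus, then Holm over feature contrasts | 77% | 73% | 70% |
| Holm over feature contrasts, no omnibus condition | 78% | 74% | 72% |
| Omnibus, then unadjusted pairs | 79% | 78% | 78% |

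The first row falls short of the fourth by 78−68 = 10, 74−56 = 18 and 72−47 = 25 points. Rows one and two isolate the omnibus condition: before rounding, it costs 0.4 to 0.6 of a point. The rest comes from the larger family. At n = 20 the first and fourth rows become 85/77/68% and 91/89/87%.

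**Sensitivity to effect size.** With a standardised difference of 0.66 (80% power for one paired t-test at n = 20) and k = 3/4/6, the omnibus test followed by Holm over all pairs gives 66/55/39%. Planned Holm contrasts give 76/72/66%, and the omnibus followed by unadjusted pairs gives 76/75/73%.

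**Sensitivity to the pattern of means.** The omnibus condition costs more if the remaining comparators lie midway between the feature and the one of interest. At 0.66, n = 20 and k = 3/6, the omnibus followed by unadjusted pairs gives 70/56%, against 80% for one unadjusted planned contrast. A planned set with Bonferroni over k−1 gives 69/55%, so against an adjusted set there is still no loss.

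**Error control if pairs are unadjusted.** Let one comparator be clearly inferior and the feature equal to the other k−2. The omnibus is then almost always significant and leaves k−2 true null feature contrasts, each tested at 5%. At n = 15 with the inferior comparator 15 points lower, the chance of at least one false feature difference is 9/12/16% for k = 4/5/6. Planned Holm contrasts give 4-5%. At k = 3 only one null contrast remains, so the error stays at 5%.

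**What a significant omnibus result shows.** Let the feature equal one comparator and lie 0.66 SD above the other (k = 3, n = 20). The omnibus is significant in 84% of trials, with no difference from the first comparator. Let two comparators instead lie 7 points below and above the feature (n = 15, SD 15, k = 3/4/5). The omnibus is significant in 80-88% of runs, and in 37/51/57% of all runs it is significant with no feature pair passing Holm over all pairs. With Holm over feature contrasts only, that figure is 36/42/45%.

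**The case against.** The strongest reply is that section 3.3 does not prescribe all pairs or any adjustment. Since section 2.1.3 describes every rating as a comparison of the feature with its comparators, limiting the follow-up to those pairs is a fair reading. This stands. A reader might infer that the plan commits itself to adjusting over all pairs; it does not, and the 10 to 25 point loss belongs to that reading alone.

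A reader might also infer that power is lost because the pairs wait for the omnibus test. In the main scenario that costs under 1 point, and unadjusted follow-up pairs are at least as powerful as the adjusted planned set.

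A third tempting inference is that the omnibus can be significant when the feature differs from none of its comparators. Apart from false positives this is impossible: if two comparators truly differ, the feature must differ from at least one of them. In the ±7 example the feature differs from both, so the 37-57% is a failure to detect, and planned contrasts barely change it at three conditions.

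Finally, section 2.1.3 states a generic expectation, "Ratings are expected to be different among different test conditions", and in section 1.2 "The primary objective of this study is to measure the subjective impression of the investigational feature", which is not worded as a comparison. An omnibus test with follow-up pairs is an orthodox analysis for an early evaluation of that kind. That lowers the weight of the point but does not remove it, because the release decision in section 1.1 rests on the feature against its comparators. The public text also does not show the number of conditions, so the size of the effect cannot be fixed.

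**Conclusion.** The point holds as a conditional one. The plan names no feature-versus-comparator contrast, and the cost depends on a choice that it leaves open:

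- Adjusted over all pairs: about 10/18/25 points of power lost with 3/4/5 conditions at n = 15.
- Unadjusted: no power lost against an adjusted planned set, but familywise error of about 9/12/16% with 4/5/6 conditions in the one-inferior-comparator case.
- One comparator, or three conditions with unadjusted pairs: essentially nothing lost.

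With four or more conditions, therefore, unrestricted pairs give up either power or error control, and planned contrasts avoid both. Separately, the omnibus result should not serve as the significant result in section 3.2, because it can arise with no feature contrast detected or with no difference from the comparator that matters. All figures rest on the assumed effect sizes, SD, alpha, number of conditions and compound symmetry. The absence of planned contrasts rests on the text alone. The change is worth making before analysis.

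**What to change.** In section 3.3:

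- State the number of conditions and alpha.
- Pre-specify within-listener contrasts of the investigational feature against each comparator.
- Test these contrasts whatever the omnibus result, with Holm or Dunnett adjustment over them only.
- Keep the omnibus ANOVA and the comparator-versus-comparator pairs as descriptive.

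In section 3.2, tie any criterion of significance to the named contrasts.

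This changes wording only and needs no extra participants or data. The downside is that comparator-versus-comparator differences lose confirmatory status, which the purpose in section 1.1 does not require. The change will not rescue a small difference: in the ±7 example at n = 15, no feature contrast is significant in 49/58/63% of runs with 3/4/5 conditions even under planned contrasts.
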